**Confidential**

sequential analysis plan using equal information increments and Pocock-type alpha spending, the sample size would have to be increased by about 15%, whereas an O'Brien-Fleming alpha spending approach would increase the total sample size by approximately 1%. The impact of the sampling plan used in this Bayesian design is likely to fall between these two approaches, so an additional 100 subjects (9%) will be accrued, bringing the total estimated sample size to 1200 as treated (AT) subjects, which should provide ample power for establishing non-inferiority in the primary hypothesis test.

## 6. Statistical Methods

### 6.1. Randomization

Randomization will follow a 1:1 allocation ratio and be stratified by site and need for revascularization, using a blocked randomization scheme with blocks of randomly varying sizes.

### 6.2. Analysis Populations

#### 6.2.1. Screening Population

All patients with symptomatic severe AS who provide informed consent will be considered screened and all available data will be entered into the Electronic Data Capture (EDC) system.

#### 6.2.2. Randomized Population

If the subject signs informed consent, meets all inclusion and none of the exclusion criteria, and the Heart Team determines the subject is suitable for randomization in the trial, then the subject is reviewed by the Screening Committee. If the subject is approved by the Screening Committee and the subject is randomized to either TAVR or SAVR, the subject is added to the randomized population. Within the randomized population the following analysis sets are distinguished:

- **The intention to treat (ITT) set:** Subjects are reported according to the randomized assignment, SAVR or TAVR, regardless of what, if any, therapy was actually received. Time zero begins at the date of randomization.
- **The as treated (AT) set:** The AT set consists of all ITT subjects with an attempted implant procedure, defined as when the subject is brought into the procedure room and any of the following have occurred: anesthesia administered, vascular line placed, TEE placed or any monitoring line placed. Subjects will be analyzed according to their first attempted procedure (TAVR or SAVR). Time zero begins at the date of the first TAVR or SAVR attempted procedure.
- **The implanted set:** The Implanted set consists of all the AT subjects who are actually implanted with either the Transcatheter Aortic Valve (TAV) or Surgical Aortic Valve (SAV). Time zero begins at the date of the first TAVR or SAVR attempted procedure.
- **The per protocol (PP) set:** The PP set is defined based on the International Council for Harmonisation (ICH) E9 Statistical Principles, which will consist of the following:
  1. All implanted subjects who were implanted according to their randomization; and
  2. Subjects without early exit (eg., lost of follow up) before 24 months (730 days), except those experiencing the primary endpoint (death or disabling stroke) prior to the early exit; and

This document is electronically controlled. Printed copies are considered uncontrolled.

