## 2. Introduction

This Statistical Analysis Plan has been designed to document, before data are analyzed, the rationale for the study design, and the planned analyses that will be included in study reports. This Statistical Analysis Plan (SAP) is developed based on the Transcatheter Aortic Valve Replacement (TAVR) Low Risk Clinical Investigational Plan (CIP).

The purpose of this trial is to evaluate the safety and effectiveness of transcatheter aortic valve replacement (TAVR) in the treatment of symptomatic severe aortic stenosis (AS) in subjects who are determined by the Heart Team to be at low surgical risk. The Low Risk trial is a multicenter, prospective, 1:1 randomized study designed to demonstrate non-inferiority (within an absolute margin of 6%) of TAVR to SAVR, as measured by a composite of all-cause death or disabling stroke rate at 24 months. The planned sample size is 1200 subjects who undergo an attempted study procedure, and the statistical methods are Bayesian. Study success will be evaluated according to an analysis plan that includes two possible interim analyses, as well as a final analysis. The first interim analysis is timed when 850 subjects have had the chance to be followed for 12 months (12 months after the 850th procedure date); a second interim analysis is timed when 1200 subjects have had the chance to be followed for 12 months (12 months after the 1200th procedure date); and the final analysis is timed when all subjects have had the chance to be followed for 24 months (24 months after the last LTI subject’s procedure date).

A study report will be prepared for submission to US Food and Drug Administration (FDA) at the time study success criteria have been met, for the purpose of seeking market approval. After all subjects have completed all protocol-specified follow-up, a final clinical report including updated long-term safety data will be prepared and submitted.

This document is electronically controlled. Printed copies are considered uncontrolled.

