### 5.2. Sample Size

Although the pre-specified analysis methods are Bayesian, the sample size is guided by a standard frequentist non-inferiority power analysis. Under the assumptions of the 15% incidence in each treatment group, non-inferiority margin  $\delta=0.06$ , 1:1 randomization,  $\alpha=0.05$ , and power = 85%, the method of Farrington and Manning as implemented in PASS 2013 indicates that the required sample size for a single-look analysis is 1032. To allow for up to 6% dropout, 1100 subjects must be accrued. Furthermore, to compensate for power lost in a three-look group

This document is electronically controlled. Printed copies are considered uncontrolled.

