**Confidential**

3. Subjects without crossover to a different type of procedure from their first attempted procedure type before their 24-month visits; and
4. Subjects must satisfy all inclusion/exclusion criteria.

Time zero begins at the date of the first TAVR or SAVR attempted procedure.

The primary analysis for the primary objective, secondary safety objectives, secondary effectiveness objectives (except for valve dysfunction, hemodynamic performance metrics, and device success) will use the AT set. Valve dysfunction, hemodynamic performance metrics, and device success will use the implanted set.

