The maximum number of non-inferiority assessments is three (first interim analysis, second interim analysis, final analysis). The maximum number of superiority assessments is two (simultaneous to passing the non-inferiority assessment for the primary endpoint and the hierarchical testing for the secondary endpoints listed in Section 6.9, or at the final analysis in the event that superiority is not established at one of the interim analyses).

The statistical approach for these analyses is Bayesian. The prior distributions for  $\pi_T$  and  $\pi_C$  in these calculations are Beta(1,1). In each analysis (interim or final), any subject with missing 24-month outcome will have that outcome predicted via a Bayesian piecewise exponential survival model that incorporates follow-up to date. Within a treatment group, let a subject's time to event follow a piecewise exponential model whose hazard function  $\lambda(\tau)$  is piecewise constant over the 3 partitioning intervals defined by the cutoff points 0, 30 days, 183 days, and 730 days. The parameters for each of the 3 intervals are assigned diffuse Gamma prior distributions, with mean 1 and variance 100, which at the time of analysis are updated based on observed data, and unobserved 24-month outcomes are predicted with probabilities determined by this model. Combining predicted and observed 24-month outcomes and integrating out the predictive distributions results in a posterior probability of non-inferiority (or superiority) that accounts for missing data as well as the uncertainty in the prediction, and this is the quantity that is compared to  $\Psi$  (or  $\Psi_{\text{SUP}}$ ) to assess non-inferiority (or superiority). This approach is similar to that taken in the SURTAVI trial, though in this case the statistical model underlying the predictions is based on a time-to-event model rather than a set of beta-binomial models. It is also similar to the approach taken in Wilber et al. The thresholds  $\Psi$  and  $\Psi_{\text{SUP}}$  are selected empirically to achieve a type I error rate (under extensive simulation) of at most 0.05 for non-inferiority testing and at most 0.025 for superiority testing.

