## 6.6. Description of Performed Analysis, per Population

The primary analysis for the primary endpoint will be performed on the AT set. In addition, it will also be performed on the ITT, Implanted, and PP sets. The inferential statistics for the following secondary endpoints will be performed on the AT set:

- The rate of the composite of death, disabling stroke, life-threatening bleed, major vascular complications, or AKI (II or III) at 30 days
- The rate of new permanent pacemaker implantation at 30 days
- The rate of prosthetic valve endocarditis at one year
- The rate of prosthetic valve thrombosis at one year
- The rate of all stroke (disabling and non-disabling) at one year
- The rate of life-threatening bleeding at one year
- The rate of valve-related dysfunction requiring repeat procedure at one year
- Quality of Life as assessed by Kansas City Cardiomyopathy Questionnaire (KCCQ) at one year
- The rate of repeat hospitalization for aortic valve disease at one year
- New York Heart Association (NYHA) functional classification at 30 days, 6 months, one year, 18 months, 2 years, 3 years, 4 years, 5 years, 7 years and 10 years
- Health-related quality of life at one year as assessed by EQ-5D survey instrument

The implanted set will be used for analyzing the primary endpoint, secondary endpoint of prosthetic valve dysfunction, device success, and echocardiographic assessment of valve performance.

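### The per-protocol set keeps early exits only if they had an event, which biases its event rate upward, and its crossover criterion is undefined

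*SAP*

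**What the plan says.** Protocol 3.3.3.2.2 leaves the PP definition to the SAP. SAP 6.2.2 sets four joint conditions:

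- **Criterion 1:** "All implanted subjects who were implanted according to their randomization; and"
- **Criterion 2:** "Subjects without early exit (eg., lost of follow up) before 24 months (730 days), except those experiencing the primary endpoint". The exception is completed by "death or disabling stroke) prior to the early exit; and".
- **Criterion 3:** "Subjects without crossover to a different type of procedure from their first attempted procedure type before their 24-month visits". It has no exception for subjects who had an event, and the SAP does not define crossover.
- **Criterion 4:** all eligibility criteria are met.

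The primary analysis of the primary endpoint uses the AT set. SAP 6.6 then says: "In addition, it will also be performed on the ITT, Implanted, and PP sets". SAP 6.5.2 states how incomplete follow-up is handled at the interim and final analyses: "any subject with missing 24-month outcome will have that outcome predicted via a Bayesian piecewise exponential survival model that incorporates follow-up to date".

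**The concern.** Among subjects who leave before day 730, PP membership depends on the primary outcome. A subject with a disabling stroke at month 6 who withdraws at month 12 stays in. A subject who is event-free and withdraws at month 12 is removed, together with 12 months of event-free follow-up. The SAP 6.5.2 model could use that follow-up, but the subject has left the set before the model is applied.

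Criterion 3 raises a related problem. If crossover means any change of modality up to 24 months, a valve that fails and is later treated by the other modality takes its subject out of the set. Protocol Appendix V, section 1.0, counts both TAVR and surgical AVR among the repeat procedures for valve dysfunction, and repeat procedure for valve dysfunction is a secondary safety endpoint. The set would then be selected on a post-procedure outcome.

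What is at stake is how far the PP analysis can be trusted as a check on the AT result. In a non-inferiority trial readers commonly look for agreement between the two.

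**Working it through.** **Inputs.** SAP 5.2: "Under the assumptions of the 15% incidence in each treatment group", up to 6% dropout, 85% power, alpha 0.05, 1:1 allocation and 1200 AT subjects (600 per arm). SAP 2: "designed to demonstrate non-inferiority (within an absolute margin of 6%) of TAVR to SAVR". Protocol 3.3.3.8 also expects up to 6% of primary data missing at 24 months.

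**Step 1: the plan's own figure.** Farrington-Manning with both rates 0.15, margin 0.06, one-sided alpha 0.05 and power 85% gives 515.2 per arm. Rounded up, 2 × 516 = 1032, which matches SAP 5.2. (One-sided 0.025 gives 1288 and does not match.) Dropout: 1032/0.94 = 1098, or about 1100. The SAP gives no figure for the PP set.

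**Step 2: expected PP rate.** Assume a constant event hazard and exits unrelated to prognosis, and measure time in units of 24 months. Under criterion 2,

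PP rate = observed events / (observed events + event-free completers).

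*Reading A: 6% would exit, uniformly over 24 months.* The event hazard is −ln(0.85) = 0.1625. The chance of an event before a uniform exit time is 1 − 0.15/0.1625 = 7.7%.

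- Events kept: 0.94 × 0.15 + 0.06 × 0.077 = 0.1456
- Set size: 0.94 + 0.06 × 0.077 = 0.9446
- PP rate: 0.1456/0.9446 = 15.4%

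*Reading B: 6% actually exit event-free, at a constant exit hazard.* Of 600 per arm, 36 are removed, 87.12 events are observed and 476.88 complete event-free. PP rate = 87.12/564 = 15.45%. If 40% of the event hazard falls in the first 30 days (assumed), it is 15.6%.

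**Step 3: the same data with exits kept.** Under Reading B the 600 subjects contribute 536.08 units of follow-up. The hazard estimate is 87.12/536.08 = 0.1625, and 1 − exp(−0.1625) = 15.0%. Using the event-free follow-up removes the bias when exits are non-informative.

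**Step 4: effect on the difference.** Both true rates are 15%, under Reading B. The arm-specific exits are assumptions with a mean of 6%.

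| Exits TAVR / SAVR | PP rate TAVR | PP rate SAVR | Difference (points) |
|---|---|---|---|
| 6% / 6% | 15.45% | 15.45% | 0.0 |
| 4% / 8% | 15.29% | 15.61% | −0.31 |
| 3% / 9% | 15.22% | 15.69% | −0.47 |
| 2% / 10% | 15.14% | 15.77% | −0.63 |

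Differences are taken before rounding. Swapping the arms reverses every sign. The zero in the first row needs equal true rates as well as equal exits. At 21% against 15% with 6% exits in both arms, the PP rates are 21.61% and 15.45%, a difference of 6.16 points against a true 6.0, which is slightly unfavourable to TAVR.

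**Step 5: criterion 3.** The documents give no crossover rate. As an illustration for either arm, take 600 subjects with 90 events.

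- Remove 1% (6 subjects) at 30% event risk: (90 − 1.8)/594 = 14.85%, down 0.15 point.
- Remove 3% (18 subjects) at 50% event risk: (90 − 9)/582 = 13.92%, down 1.08 points.

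The shift lowers the rate of whichever arm loses the subjects.

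**The case against.** **No trial decision rests on the PP set.** Success is judged on the AT set. The SAP attaches no agreement rule or claim to the PP result. The AT, ITT and Implanted analyses all keep the subjects at issue, so a reader can see what criteria 2 and 3 do by comparing sets. This stands, and it limits the importance of the point. It does not make the PP rule sound.

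**The exception in criterion 2 is necessary.** Death is itself an exit, and dropping subjects who died would be worse. This also stands: the fault lies in discarding event-free follow-up, not in keeping events.

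**A complete-case set has a use.** It is the one set in which dropouts' outcomes are not model-predicted at the final analysis. That is fair, and it argues for keeping the current version under a clear label.

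**A reader might infer that the PP set is tilted toward TAVR.** The argument would be that SAVR loses more subjects and that criterion 3 removes mainly TAVR failures, because the protocol forbids crossover from SAVR to TAVR. The documents support neither step. They give no arm-specific exit rates, and subjects who never reach the procedure room cannot be in the PP set, since criterion 1 admits only implanted subjects. The prohibition in Protocol 3.3.8 concerns treatment after assignment and device dispensation. It does not address later re-intervention on a failed valve, and Appendix V lists TAVR among the possible repeat procedures.

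**Conclusion.** The point holds as a bias in a supportive analysis. Criterion 2 raises the expected PP event rate from 15% to about 15.4% to 15.5% at the planned 6% dropout, given a constant hazard and exits unrelated to prognosis. The bias in the difference is zero with equal exits and equal true rates. It is about 0.3 to 0.6 point in favour of the arm with fewer exits for assumed splits of 4%/8% to 2%/10%, against a margin of 6 points. Its direction cannot be determined from the documents.

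A full 1-point bias would need a split such as 2% in TAVR and 15% in SAVR (15.1% against 16.1% under Reading A). That averages 8.5% and goes well beyond the planned 6%, so it should not be taken as the expected size.

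Criterion 3 is ambiguous. Read broadly, it removes later other-modality re-interventions, which can occur in either arm. Its size depends wholly on assumed crossover rates. The AT primary result, alpha and sample size do not change.

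**What to change.** In SAP 6.2.2:

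1. Delete criterion 2. Early exits stay in the PP set, their events are counted, and any missing 24-month outcome is predicted from follow-up to date by the SAP 6.5.2 model.
2. In criterion 3, define crossover as a change of modality at the index procedure, so that later other-modality re-interventions stay in. The narrowed criterion overlaps largely with criterion 1, but it removes the ambiguity.
3. If wanted, keep the current complete-case version as a labelled sensitivity analysis.

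The cost is SAP wording only: no new data and no new model. The downside is that the PP set then relies on model prediction for dropouts and moves closer to the Implanted set, differing mainly by eligibility violations and index crossovers.

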**Confidential**

3. Subjects without crossover to a different type of procedure from their first attempted procedure type before their 24-month visits; and
4. Subjects must satisfy all inclusion/exclusion criteria.

Time zero begins at the date of the first TAVR or SAVR attempted procedure.

The primary analysis for the primary objective, secondary safety objectives, secondary effectiveness objectives (except for valve dysfunction, hemodynamic performance metrics, and device success) will use the AT set. Valve dysfunction, hemodynamic performance metrics, and device success will use the implanted set.

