### 3.3.12 Implant Procedure (TAVR)

The implantation procedure is performed according to the standard procedures of the implanting physicians. In countries where required, specifically the United States and Japan, the local heart team's interventional cardiologist(s) and cardiac surgeon(s) must jointly participate in the intra-operative technical aspects of the TAVR procedure. Procedural aspects specific to the Medtronic TAVR system should be performed according to the Instructions for Use, with the exception of the use of pre-deployment balloon aortic valvuloplastyvii. The following variables will be collected regarding the TAVR implantation procedure:

- Name of the primary and secondary operator
- Anesthesia type (general or local)
- Delivery catheter access site and vessel diameter of access site
- Use of EnVeo InLine Sheath alone, OR use of separate introducer sheath size and type
- Pre-deployment BAV (yes/no)
- Use of rapid pacing during BAV and deployment (yes/no)
- Size of TAV implanted
- Post-implant dilation (yes/no)
- Post-implant pressures at final result (LV systolic and end-diastolic, aortic systolic and diastolic)
- Implantation of TAV within the desired location (yes/no)
- Post-implant degree of prosthetic regurgitation by angiography (Sellers criteria)
- Post-implant degree of prosthetic paravalvular regurgitation by TEE, if performed
- Post-implant degree of prosthetic transvalvular regurgitation by TEE, if performed
- More than one TAV implanted (yes/no)
- Patency of coronary arteries post-implant (yes/no)
- Estimated contrast volume used
- Total procedural time (minutes): time in procedure room to exit from procedure room
- Information on use of resheath/recapture featureviii
- Occurrence of adverse events
- If TAV implantation not attempted, reason why

---

vii For this trial, the use of pre-deployment BAV is per the discretion of the implanting physician. It will not be considered a deviation if pre-deployment BAV is not performed.

viii Definitions of resheath/recapture use are provided in Appendix IV.

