## Notes:

1. DVI = Doppler Velocity Index (LVOT VTI/valve VTI)
  2. For subjects with BSA <1.6 m^2, the EOA criteria for significant (moderate or severe) stenosis is <0.6 cm^2
  3. For subjects with LVOT diameter >2.5 cm, the DVI criteria for significant (moderate or severe) stenosis is <0.2 cm^2
  4. Reporting of prosthetic valve dysfunction will be based on core lab results.
  5. Prosthetic valve dysfunction events are not reported as adverse events, unless the dysfunction is accompanied with clinical sequelae at the time of event detection, and the clinical sequelae are chronologically and physiologically associated with the dysfunction. However, prosthetic dysfunctions that are associated with adverse events, and that meet the definition of a serious adverse event, should be reported as such.
- Quality of Life as assessed by Kansas City Cardiomyopathy Questionnaire (KCCQ) at 30 days and one year  
The endpoint will be evaluated using a Bayesian analog of a two-sample t-test. Descriptive statistics for KCCQ change from baseline will also be reported at 30 days, 6 months, one year, and annually through 5 years.
  - The rate of repeat hospitalization for aortic valve disease at one year.  
The incidence estimate will be provided for the two treatment groups at the specified time point. The statistical method will be the Bayesian version of analysis for comparing proportions. In addition, the Kaplan-Meier estimates will be provided at the following time points: 30 days, 6 months, 12 months, 18 months, and annually thereafter through 10 years.
  - Device Success (VARC II), defined as
    - Absence of procedural mortality, AND
    - Correct positioning of a single prosthetic heart valve into the proper anatomical location, AND
    - Intended performance of the prosthetic heart valve, defined as the absence of patient-prosthesis-mismatch and mean aortic valve gradient less than 20 mmHg (or peak velocity < 3 m/sec), AND absence of moderate or severe prosthetic valve regurgitation.

The incidence estimate will be provided for the TAVR group.

The criteria for ECHO will be based on the ECHO Core Lab Data:

- Absence of patient-prosthesis-mismatch
  1. For subjects with BMI < 30 kg/m^2, index effective orifice area (EOAi) > 0.85 cm^2 /m^2
  2. For subjects with BMI ≥ 30 kg/m^2, index effective orifice area (EOAi) > 0.70 cm^2 /m^2

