**Confidential**

- Mean aortic gradient < 20 mmHg or peak velocity < 3 m/sec;
- Absence of moderate or severe prosthetic valve regurgitation. Total Aortic Prosthetic Regurgitation on the ECHO CORE LAB form not equal to moderate or severe.

All of the above components must be satisfied to count as a device success. If any of the above components fails, the endpoint will be counted as a failure.

For the overall device success rate, the numerator will be the number of subjects whose procedures result in device success as described above, and the denominator will be the number of subjects whose device success results are not missing (either success or failure). Note that this analysis excludes those subjects with a missing response to any of the above five components (eg, the field “Post-implant Severity of Total Aortic Regurgitation”=“Unable to Assess” or “Not Recorded”, missing mean aortic gradient, or missing peak velocity, etc.) and without a “NO” response to any of the components.

- Hemodynamic performance metrics by Doppler echocardiography
  - Mean aortic gradient at one year
  - Effective orifice area at one year
  - Degree of total, peri, and transvalvular prosthetic regurgitation at one year

For mean gradient and effective orifice area, the descriptive statistics will be reported at each of the assessed time point (30 days, 6 months, one year, 2 years, 3 years, 4 years, 5 years, 7 years and 10 years). The statistical method will be the Bayesian version of a two-sample t-test.

Prosthetic regurgitation severity will be reported as proportions at each of the assessed time point (30 days, 6 months, one year, 2 years, 3 years, 4 years, 5 years, 7 years and 10 years). The statistical method will be the Bayesian version of a comparison of proportions.

- New York Heart Association (NYHA) functional classification at one year

NYHA function classification will be reported as proportions at each of the assessed time point (30 days, 6 months, one year, 2 years, 3 years, 4 years, 5 years, 7 years and 10 years). The statistical method will be the Bayesian version of a comparison of proportions.

- Health-related quality of life as assessed by EQ-5D survey instrument at one year.

The endpoint will be evaluated using a Bayesian analog of a two-sample t-test.

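### In the randomized trial, device success leaves out TAVR attempts that end with no valve, although such attempts cannot meet the endpoint's positioning component

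*SAP*

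**What the plan says.** **Analysis sets.** Protocol 3.3.3.2.2 and SAP 6.2.2 both take device success out of the AT set by name: "Valve dysfunction, hemodynamic performance metrics, and device success will use the implanted set". The implanted set is the part of the AT set "who are actually implanted with either the Transcatheter Aortic Valve (TAV) or Surgical Aortic Valve (SAV". SAP 6.6 repeats the choice: "The implanted set will be used for analyzing the primary endpoint, secondary endpoint of prosthetic valve dysfunction, device success". Entry to the AT set needs only that the subject is in the procedure room and that anesthesia, TEE or a line has been started. No AT or ITT version of device success is planned.

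**Endpoint.** SAP 6.8 asks for no procedural death, then "Correct positioning of a single prosthetic heart valve into the proper anatomical location", then several core-lab echo criteria. It adds: "If any of the above components fails, the endpoint will be counted as a failure". The rate is given for the TAVR group only.

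**Missing results.** Under SAP 6.8 the denominator is subjects with a known result. A subject is left out only when some component is missing and no component carries a NO.

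**Data on these cases.** Protocol 3.3.11 keeps subjects who are taken to the procedure room but receive no valve in follow-up for the whole trial. Protocol 3.3.12 collects the positioning item, "Implantation of TAV within the desired location (yes/no", separately from "If TAV implantation not attempted, reason why".

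**The concern.** The set and the endpoint do not fit together. The positioning component describes the outcome of the attempt, and SAP 6.8 words the numerator in terms of what the procedure achieved. An attempt with no valve has no correctly positioned valve. The implanted-set restriction nevertheless removes it before the failure rule can be applied, and nothing later puts it back.

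Such cases are foreseeable. Protocol 2.1 describes recapture as a way to reposition or remove the prosthesis, and Protocol 3.3.11 provides for subjects who leave the procedure room without a valve.

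At stake is how a secondary effectiveness rate is read. A reader who takes it as the chance that a TAVR attempt succeeds would be given a figure that can err only in the device's favor.

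**Working it through.** **1. The plan's own figures.** The documents state no expected device success rate and no expected number of no-valve attempts, so there is no device success figure to reproduce. Only the denominator comes from the plan. Its single-look sample size of 1032 reproduces with the Farrington-Manning formula (516 per arm). Dividing by 0.94 for dropout gives 1098 against the stated 1100, and the plan adds 100 to reach 1200 AT subjects (SAP 5.2). At 1:1 this is n = 600 TAVR attempts. Half of the 1540 randomization cap in Protocol 3.3.4 is n = 770, if all are attempted.

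**2. What happens to each kind of TAVR attempt under the current text.**

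| Outcome of the attempt | In implanted set? | Scored as |
|---|---|---|
| TAV implanted, all components met | yes | success |
| TAV implanted, then procedural death, malposition, second valve or failed echo criterion | yes | failure |
| Converted, surgical valve implanted | yes (the set accepts either valve) | not stated |
| No valve of either type | no | not scored |

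Only the last row leaves the analysis.

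**3. Size.** Let n be TAVR attempts, k those with no valve, and s the success rate among implanted subjects, ignoring other missing results.

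- Successes = s(n − k)
- Reported rate = s
- Rate per attempt = s(n − k)/n
- Overstatement = s × k/n

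Both s and k are assumptions. The overstatement in percentage points is:

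| k/n | s = 80% | s = 90% | s = 95% |
|---|---|---|---|
| 0 | 0 | 0 | 0 |
| 1% | 0.80 | 0.90 | 0.95 |
| 2% | 1.60 | 1.80 | 1.90 |
| 3% | 2.40 | 2.70 | 2.85 |

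Example: n = 600, k = 18, s = 95% gives 95.0% reported against 0.95 × 582/600 = 92.15% of attempts.

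If m implanted subjects are also dropped for missing results, the overstatement becomes s × k/(n − m), which is slightly larger.

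**4. Against sampling error.** The 95% half-width is 1.96 × √(s(1 − s)/n). The overstatement exceeds it once k/n is above half-width/s.

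| n | s | Half-width (points) | Break-even k/n | Exceeded from k = |
|---|---|---|---|---|
| 600 | 80% | 3.20 | 4.00% | 25 |
| 600 | 90% | 2.40 | 2.67% | 17 |
| 600 | 95% | 1.74 | 1.84% | 12 |
| 770 | 80% | 2.83 | 3.53% | 28 |
| 770 | 90% | 2.12 | 2.35% | 19 |
| 770 | 95% | 1.54 | 1.62% | 13 |

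At s = 80% the break-even share lies outside the assumed 0 to 3% for both values of n.

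**The case against.** The strongest reply is that the choice is deliberate and consistent. Protocol and SAP name the same set, the echo components need a valve to measure, and nothing calls the rate a rate per attempt. The agreement is real: this is a mismatch between endpoint and set, not a contradiction between documents. The echo argument justifies the implanted set for valve dysfunction and hemodynamics. It does not carry device success, because SAP 6.8 keeps a subject with missing echo as a failure when another component is a NO.

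Second, the AT set is not a clean denominator either. A case cancelled after a line was placed, before any device was introduced, is not clearly a device failure. That stands, and it is why both rates and separate counts are needed.

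Third, the documents do not say whether a no-valve attempt would carry a NO or a blank on the positioning item, and the case report forms are separate documents (Protocol 3.1.3). That also stands. Changing the set alone might not work, because a blank could be excluded again as missing.

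Fourth, part of the information is visible already. Deaths in these attempts count in the AT analyses of the primary endpoint and the 30-day composite, and SAP 6.3 summarizes baseline data by arm for both sets, so the gap in numbers can be inferred. The plan does not connect that gap to the device success rate.

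**Conclusion.** The point holds for the randomized trial and is minor. As a rate per TAVR attempt, the planned figure is too high by about s × k/n: 0 to about 2.9 percentage points under assumed k/n of 0 to 3% and s of 80 to 95%. It is zero if every attempt ends with a valve, and often within sampling error. The direction is certain; the size rests wholly on assumptions.

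A reader might infer more than the documents support:

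- **That a tested claim is affected.** Device success is descriptive, TAVR only and absent from the ordered list in SAP 6.9. Type I error, power and labeling tests do not depend on it.
- **That the mortality component also fails all of these attempts.** It fails only those in which the subject dies. The positioning component is the one that no such attempt can meet.
- **That conversions to surgery drop out.** A converted subject who receives a surgical valve stays in the implanted set. What is missing there is a scoring rule.
- **That the continued-access study has the same defect.** It also uses its implanted set, but Continued Access SAP 7.7.3 measures endpoints by registry (TVT-R) definitions that the documents do not give. No mismatch can be shown there.

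**What to change.** In SAP 6.2.2, 6.6 and 6.8, and in Protocol 3.3.3.2.2 at the next amendment:

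1. Report device success for AT subjects whose first attempted procedure was TAVR.
2. State in SAP 6.8 that an attempt without a single correctly positioned TAV, including conversion to a surgical valve, counts as a failure and is not removed by the missing-response exclusion.
3. Keep the implanted-set rate beside it. Report the numbers of no-valve attempts, conversions, and cases cancelled before any device was introduced.

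The second step is essential, since without it a blank positioning field could undo the first.

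The cost is SAP wording, a few lines of code and one extra table row. The subjects are already in the AT set and in follow-up. A protocol edit has to pass through the amendment process in Protocol 3.3.25, so it should wait for an amendment that is being made anyway. The downside is a slightly lower rate that may include a few early-cancelled cases, which the separate counts make visible.
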